10 SAFETY ANALYSES

All safety analysis will be performed for SS-s and SS-a.

10.1 Extent of exposure

Extent of exposure is not relevant for the DV0004 substudy. Occurrence of adverse device effects in this substudy will not be affected by the duration of medication exposure.

10.2 Adverse events

All AEs (including serious adverse events [SAEs]) will be reported in a common database for PA0012 and DV0004, but only adverse device effects (ADEs), serious adverse device effects (SADEs), and device deficiencies will be summarized in the DV0004 substudy. Specifically, only those AEs related to the use of the investigational medical devices bimekizumab-SS-1mL or bimekizumab-AI-1mL (based on the Investigator's judgement) will be assessed. All AEs (including SAEs) which are not assessed to be related to the investigational devices will be summarized separately in the report for the main PA0012 study. An exception are AEs that are indicated as injection site reactions during self-injection. These will be listed in DV0004 as well as in PA0012.

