11 ASSESSMENT OF SAFETY

11.1 Adverse events (device presentations)

All AEs (including serious adverse events [SAEs]) will be reported in a common database for PA0012 and DV0004, but only ADEs, SADEs, and device deficiencies will be summarized in the DV0004 substudy. Specifically, only those AEs related to the use of the device presentations bimekizumab-SS-1mL or bimekizumab-AI-1mL (based on the Investigator's judgement) will be assessed. All AEs (including SAEs) which are not assessed to be related to the device presentations will be summarized separately in the report for the main study, PA0012; please refer to the PA0012 protocol for information on reporting and recording AEs (including SAEs).

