11.1.1.3 Device deficiency (device presentations)

A device deficiency is an inadequacy of a medical device with respect to its identity, quality, durability, reliability, safety, or performance. Device deficiencies include malfunctions, use errors, and inadequate labeling.

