11.1.2.2 Reporting of device deficiencies

If a device deficiency related to the identity, quality, durability, reliability, safety, or performance of the device presentation is reported (even if the device presentation was not used), UCB must be informed within 1 business day (within 24 hours, as a rule) of receipt of this information by the site. The Investigator must forward to UCB (or designee) a duly completed Investigator Adverse Device Effect and Device Deficiency form provided by UCB, even if the data are incomplete or if it is obvious that more data will be needed to draw any conclusions.

An Investigator Adverse Device Effect and Device Deficiency form will be provided to the Investigator. The Investigator Adverse Device Effect and Device Deficiency form must be completed in English.

It is important for the Investigator, when completing the Investigator Adverse Device Effect and Device Deficiency form, to include an assessment and documentation of whether the device deficiency could have led to an SAE if any of the following occurred:

- Suitable action had not been taken, or
- Intervention had not been made, or
- Circumstances had been less fortunate.

All defective devices must be returned to UCB according to standard procedures (see Section 7.6).

11.1.2.3 Reporting of serious adverse device effects including device deficiencies with risk of serious adverse event

If a device deficiency that could have led to an SAE (if suitable action had not been taken, or intervention had not been made, or circumstances had been less fortunate) is reported, UCB must be informed within 24 hours of receipt of this information by the site (see contact information for SAE reporting listed in the Serious Adverse Event Reporting section at the front of the protocol). The Investigator must forward to UCB (or designee) a duly completed "Investigator SAE Report Form for Investigational Medical Devices" provided by UCB, even if the data are incomplete, or

if it is obvious that more data will be needed to draw any conclusions. Information recorded on this form will be entered into the global safety database.

An Investigator SAE Report Form for Investigational Medical Devices will be provided to the Investigator. The Investigator SAE Report Form for Investigational Medical Devices must be completed in English.

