10.2.1 Adverse device effects

Adverse events are recorded at the AE CRF page at the time when they occur. If an AE is related to the device by assessment of the investigator it is counted as an ADE.

All ADE data will be listed, and no statistical testing will be performed. Only treatment-emergent ADEs will be included in the summary tables. Treatment-emergent ADEs (TEADEs) will be defined as events related to the study device that have a start date on or following the first self. administration of study treatment in DV0004 through the final self-administration of study treatment + 7 days. The device SFU will occur 1 week after the last self-administration.

All ADEs will be coded and classified by system organ class, high level term, and preferred term. Adverse device effects will be summarized by the frequency and percentage of subjects having 1 or more of the events in question. Additional planned summaries include overall ADEs and SADEs. Summaries to be presented include:

- Incidence of TEADEs – Overview
- Incidence of TEADEs by SOC, HLT, and PT
- Incidence of serious TEADEs by SOC, HLT, and PT
- Incidence of TEADEs leading to death
- Incidence of TEADEs leading to discontinuation
- Incidence of non-TEADEs (only listed and not summarized in a table)

For definition of serious, unanticipated and unanticipated serious ADEs (USADEs) see protocol of DV0004.

Adverse device effects which started before DV0004 Week 4 and were ongoing at the data cut off will be included with the status remaining as ongoing. Adverse device effects which were ongoing at DV0004 Week 4 but with an end date before the data cut off will be included with their end date as recorded.

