11.3 Other outcome variables

The other outcome variables will be summarized using descriptive statistics and they will be tabulated separately for each device using the relevant FAS population.

Assessments where the self-injection was not performed by the subject will not be included in any summary statistics.

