11.3.4 Structural and mechanical integrity of the devices

The structural and mechanical integrity of the device after completion of self-injection will be assessed by the investigator after each injection in the “Subject self-injection of bimekizumab” CRF page. The assessment will be done using the questions for structural integrity. The structural integrity is based on a visual examination of the device that shows clear evidence of damage, compromised structural or mechanical integrity not superficial and/or cosmetic imperfections.

Frequency tables will be produced to show the number and percentage of devices with used bimekizumab-SS-1mL and bimekizumab-AI-1mL syringes identified as having structural integrity issues after completion of self-injection.

The 90% CIs based on the Exact Binomial method will be reported as well.

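### No planned output delivers the promised summary of device deficiencies, and a rule in SAP 11.3 can drop a failed device from the integrity tables because someone else then gave the injection

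*SAP*

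**What the plan says.** Both documents commit to a summary of device deficiencies. SAP 10.2 says that all adverse events are held in a common database, "but only adverse device effects (ADEs), serious adverse device effects (SADEs), and device deficiencies will be summarized in the DV0004 substudy". Protocol 11.1 says the same: "but only ADEs, SADEs, and device deficiencies will be summarized in the DV0004 substudy".

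Protocol 11.1.1.3 defines the term broadly: "Device deficiencies include malfunctions, use errors, and inadequate labeling". Collection is also broad. Under Protocol 11.1.2.2, if a deficiency "is reported (even if the device presentation was not used), UCB must be informed within 1 business day", and a dedicated form must be completed.

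The planned safety outputs are narrower. After the general statement "Additional planned summaries include overall ADEs and SADEs", SAP 10.2.1 lists only outputs for adverse device effects. Protocol 14.5 likewise plans only adverse device effects and their serious subset.

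Device performance is tabulated in SAP 11.3.4, for devices "identified as having structural integrity issues after completion of self-injection", and in SAP 11.3.5, for devices found functionally compromised. The parent section, SAP 11.3, adds a rule that applies to both: "Assessments where the self-injection was not performed by the subject will not be included in any summary statistics".

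**The concern.** The trial exists to evaluate two device presentations, so how often each one fails is a main result. A promised summary with no table, unit of count or denominator may not be produced, or may be designed after the data are known.

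The exclusion in SAP 11.3 is the sharper problem. For the questionnaire and the pain scale, who injected matters, because those variables describe the subject's own experience. For the device it does not. If a device fails and another person then gives the dose, the failure itself is the reason the assessment is removed. A measure of device failure should not lose observations because the device failed.

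**Working it through.** **No figure to reproduce.** The documents state no expected deficiency rate, target or margin, and the study is descriptive and unpowered (SAP 2.4). The check is mainly a comparison of text.

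**Where each kind of event would be counted:**

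| Event | Planned summary |
|---|---|
| Subject starts, dose incomplete | Non-success in the primary table (SAP 11.1) or secondary table (SAP 11.2), not labelled as a deficiency; possibly SAP 11.3.5 |
| Use error causing an adverse event | Tables of treatment-emergent adverse device effects (definition in SAP 2.2.1.3.4, outputs in SAP 10.2.1) |
| Use error, complete dose, no adverse event, no visible fault | None specified |
| Fault found before use | None specified |
| Labelling fault | None specified |
| Device fails, another person then injects | Can be removed from SAP 11.3.4 and 11.3.5 by the SAP 11.3 rule |

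The same exclusion sentence appears in SAP 11.1 and 11.2. The primary and secondary tables are therefore not a reliable back-up for the last row.

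The adverse-effect tables cannot fill the gap either. An adverse device effect is by definition an adverse event, so a malfunction without one is a deficiency and nothing else.

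**Illustration of size (counts assumed).** Inputs:
- about 100 subjects per arm (SAP 2.3.6);
- two self-injections each (Protocol 7.2), so at most about 100 × 2 = 200 devices per arm;
- 90% exact binomial intervals (SAP 11.3.4 and 11.3.5).

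For x events in n devices, the lower limit is the 0.05 quantile of Beta(x, n − x + 1), and the upper limit is the 0.95 quantile of Beta(x + 1, n − x). For x = 0 the lower limit is 0 and the upper is 1 − 0.05^(1/n). With n = 198 this is 1 − 0.05^(1/198) = 1.50%.

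Suppose k failed devices leave the table and no other device shows a fault:

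| k (assumed) | Table as planned | All devices counted |
|---|---|---|
| 1 | 0/199 = 0% (0 to 1.49%) | 1/200 = 0.5% (0.03 to 2.35%) |
| 2 | 0/198 = 0% (0 to 1.50%) | 2/200 = 1.0% (0.18 to 3.11%) |
| 4 | 0/196 = 0% (0 to 1.52%) | 4/200 = 2.0% (0.69 to 4.52%) |
| 10 | 0/190 = 0% (0 to 1.56%) | 10/200 = 5.0% (2.74 to 8.33%) |

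Whatever k is, the planned table reads 0% with an upper limit near 1.5%. It gives no sign that anything was removed.

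**The case against.** A reader might infer that every deficiency that stops an injection, and every use error, goes uncounted, so that device reliability is overstated. The documents do not support this.

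- Success in SAP 11.1 requires a complete dose, and SAP 11.2 is analysed in the same way. A jam that leaves the subject's own dose incomplete therefore lowers a tabulated rate with an interval.
- Use errors that cause an adverse event enter the adverse-device-effect tables.
- SAP 11.3.5 is assessed after each injection and includes devices that do not work as they should, so partly used devices may be captured.
- SAP 3.1 promises listings of all documented data.

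These points narrow the gap but do not close it. A listing is not the promised summary, and a primary-endpoint failure is not attributed to the device.

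Further points on the other side also have force. The exclusion reaches a failed attempt only if that attempt is recorded as not performed by the subject, and the eCRF that would show this is not among the documents. The protocol itself defines integrity after completed self-injection (Protocol 3.3 and 4.1.3.1), and its Section 14.5 omits deficiencies too, so the SAP has not departed from it. Suspension decisions under Protocol 13.4 are served by rapid reporting and ongoing review, so a missing end-of-study table does not impair them. Finally, the documents do not show that the deficiency form records type of deficiency.

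What remains is that the exclusion rule is written without qualification and applies to the device tables, and that no output meets the commitment in SAP 10.2.

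**Conclusion.** The point holds in a limited form. Device deficiencies are to be summarised and no output does so. The exclusion in SAP 11.3 can remove a failed device from the integrity percentages when another person then injects. Failures before use, labelling faults, and use errors with a complete dose and no adverse event have no specified device-performance summary.

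The direction of any effect is towards understating device failure. Its size cannot be established. The figures above rest on assumed counts, on all of those failures being excluded, and on no other fault being seen. To say that reliability is overstated would go beyond the documents; it may be, if such events occur and are recorded in a way that triggers the rule.

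**What to change.** 1. In SAP 11.3, exempt 11.3.4 and 11.3.5 from the exclusion for injections not performed by the subject. Count every assigned DV0004 device on which a subject started or attempted an injection, in both numerator and denominator. Show the protocol-defined figure, after completed self-injection, alongside. Record the addition in SAP 3.8.
2. In SAP 10.2, add one table per device presentation giving the number of devices and of subjects with a deficiency. Include whether each deficiency might have resulted in a serious adverse event, which Protocol 11.1.2.2 already requires on the form. Add type (malfunction, use error, labelling) where it is captured. List unused defective devices separately.

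The cost is one more table per device presentation, a short change to SAP 11.3, and some reconciliation of deficiency forms with the clinical database. The reported device failure percentages may be slightly less favourable.

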10.2.1 Adverse device effects

Adverse events are recorded at the AE CRF page at the time when they occur. If an AE is related to the device by assessment of the investigator it is counted as an ADE.

All ADE data will be listed, and no statistical testing will be performed. Only treatment-emergent ADEs will be included in the summary tables. Treatment-emergent ADEs (TEADEs) will be defined as events related to the study device that have a start date on or following the first self. administration of study treatment in DV0004 through the final self-administration of study treatment + 7 days. The device SFU will occur 1 week after the last self-administration.

All ADEs will be coded and classified by system organ class, high level term, and preferred term. Adverse device effects will be summarized by the frequency and percentage of subjects having 1 or more of the events in question. Additional planned summaries include overall ADEs and SADEs. Summaries to be presented include:

- Incidence of TEADEs – Overview
- Incidence of TEADEs by SOC, HLT, and PT
- Incidence of serious TEADEs by SOC, HLT, and PT
- Incidence of TEADEs leading to death
- Incidence of TEADEs leading to discontinuation
- Incidence of non-TEADEs (only listed and not summarized in a table)

For definition of serious, unanticipated and unanticipated serious ADEs (USADEs) see protocol of DV0004.

Adverse device effects which started before DV0004 Week 4 and were ongoing at the data cut off will be included with the status remaining as ongoing. Adverse device effects which were ongoing at DV0004 Week 4 but with an end date before the data cut off will be included with their end date as recorded.

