5.2 Schedule of study assessments

The schedule of assessments for DV0004 is presented in [Table 5-1](#) and includes assessments performed specifically in the DV0004 substudy. The schedule of assessment for PA0012 Entry Visit through Week 8 is presented in [Table 5-2](#) and includes assessments performed as part of the PA0012 study.

PUBLIC COPY
This document cannot be used to support any marketing authorization application and any extensions or variations thereof.

Table 5–1: Schedule of study assessments for DV0004

Visit ^a Week	Visit 1	Visit 2	Visit 2a Telephone Call (Device SFU)
	Baseline/ Feeder Study Final Visit	Week 4	Week 5
Procedures			
Informed consent for DV0004 assessments	X		
Inclusion/exclusion	X		
Concomitant medication	X	X	X
Adverse events ^b	X	X	X
Random assignment to device presentation	X		
IRT contact	X	X	X
Subject training for VAS and SIAQ Questionnaire	X		
Pre-injection SIAQ Questionnaire ^c	X		
Subject training for self-injection	X		
Subject self-injection of bimekizumab using the assigned device presentation	X	X	
Study personnel evaluation of self-injection	X	X	
Study personnel evaluation of post-use device presentation for visual signs of structural or mechanical integrity (such as cracks or loose parts) ^c	X	X	
VAS for injection site pain	X	X	
Post-injection SIAQ Questionnaire ^c	X	X	
Drug and device presentation accountability	X	X	

IRT=interactive response technology; SFU=safety follow-up; SIAQ=Self-injection Assessment Questionnaire; VAS=visual analog scale

^a Visit windows are ±7 days from the scheduled visit day (relative to the first dose) at all visits except Visit 2a (SFU telephone call). The SFU telephone call window is 7 days from the last dose in the DV0004 substudy, ±3 days.

Table 5–1: Schedule of study assessments for DV0004

Procedures	Visit ^a Week	Visit 1	Visit 2	Visit 2a Telephone Call (Device SFU)
			Baseline/ Feeder Study Final Visit	Week 4

^b Adverse events not related to the device presentations will be reported in PA0012 and adverse device effects and device deficiencies will be reported in DV0004. A single safety database will be used for both studies.

^c Version 2.0 of the SIAQ will be used to assess bimekizumab-SS-1mL, while version 2.1 will be used to assess bimekizumab-AI-1mL (see Section 9.1).

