3 DATA ANALYSIS CONSIDERATIONS

3.1 General presentation of summaries and analyses

Statistical analysis and generation of tables, figures, subject data listings, and statistical output will be performed using SAS Version 9.3 or higher. All tables and listings will use Courier New font size 9.

Descriptive statistics will be displayed to provide an overview of the study results. For continuous variables, descriptive statistics will include number of subjects with available measurements (n), mean, standard deviation (SD), median, minimum, and maximum.

For categorical variables, the number and proportion of subjects, will be presented. In addition, for the primary, secondary and other variables the 90% confidence interval (CI) based on the Exact Binomial, will also be presented. Unless otherwise noted, the denominator for percentages should be based on the number of subjects included in the respective analysis set. Subjects with missing data can generally be accounted for using either of the following approaches:

- For summaries of demographics and Baseline characteristics: summarize percentages based on all subjects in the analysis set and include a “Missing” category (corresponding to subjects with missing data for the variable being summarized) as the last row in the list of categories being summarized.
- For summaries of outcome and safety variables, unless otherwise specified: percentages will be summarized based only on those subjects with observed data for the variable being summarized. As the denominator may be different from the number of subjects in the analysis set being considered, the denominator should be displayed in the table. The general format for displaying this will be “n/NSub (%)”, unless otherwise specified.

Percentages will be presented to 1 decimal place. If the percentage is 100 or 0, no decimal will be presented. Typically, the % sign should be presented in the column header, but not with each individual value.

For bimekizumab PK concentrations, summary statistics will include geometric mean, geometric coefficient of variation (CV), 95% confidence intervals for geometric mean, arithmetic mean, SD, median, minimum, and maximum. All summaries of PK variables will be based on the observed values. No imputation will be used.

Decimal places for descriptive statistics will always apply the following rules:

- “n” will be an integer

- Mean, SD, and median will use one additional decimal place compared to the original data

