10.2.2 Impact of COVID-19 on adverse events

In order to assess the impact of the COVID-19 global pandemic on the primary safety endpoint of incidence of TEADEs and serious TEADEs, additional summaries will be presented. Summaries of TEADEs and Serious TEADEs will be presented by COVID-19 enrollment period and timing of the ADE relative to the WHO declared COVID-19 pandemic (enrolled prior to pandemic – ADE prior to pandemic, enrolled prior to pandemic – ADE during pandemic, enrolled during pandemic – ADE during pandemic), as defined in Section 4.9.1. ADEs leading to discontinuation will be presented by COVID-19 enrollment period and timing of ADE relative to the pandemic period as well.

For reporting purposes, AEs will be assigned to ‘Prior to COVID-19 pandemic’ or ‘During the COVID-19 pandemic’ based on the following:

- If the date of AE or ADE onset (based on imputed start date) is prior to 11 March 2020 the AE/ADE will be assigned as ‘Prior to COVID-19 pandemic’
- If the date of AE or ADE onset (based on imputed start date) is on or after 11 March 2020 the AE/ADE will be assigned as ‘During the COVID-19 pandemic’

A ‘Post the COVID-19 pandemic’ phase will not be assigned for AE reporting as the pandemic is expected to be ongoing at the time of last subject last visit.

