11.1 Primary outcome variable

The primary outcome variable is the percentage of all subjects able to self-administer safe and effective injections using the given device at DV0004 Week 4. Safe and effective self-injection will be evaluated by the study personnel as defined below:

- Complete dose delivery: Subject self-injects the complete dose of bimekizumab as confirmed by a visual inspection of the bimekizumab-SS-1mL or the bimekizumab-AI-1mL which shows that the IMP is delivered completely (i.e., the container is empty), and
- No ADEs that would preclude continued use of the device presentations for self-injection (i.e., no SADEs and/or ADEs leading to withdrawal from the DV0004 substudy).

All data to assess the primary outcome is collected on the subject self-injection of bimekizumab CRF page for DV0004 Week 4. For the number of subjects with safe and effective self-injections simply the cases which indicated “yes” for the question “Did the subject self-inject the complete dose of Bimekizumab” and “no” for the question “Were there any AEs related to use of the investigational device for self-injection” at DV0004 Week 4 are counted.

The number and percentage of subjects with safe and effective self-injections will be tabulated separately for each device presentation using the relevant FAS population (FAS-s or FAS-a). The 90% CIs based on the Exact Binomial method will be reported as well. The number and percentage of subjects with safe and effective self-injections is tabulated for each device presentation by COVID-19 enrollment period, as described in Section 4.9.1.

Assessments where the self-injection was not performed by the subject will not be included in any summary statistics.

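### A device effect that starts more than 7 days after Baseline and stops the Week 4 self-injection is left out of the table of device effects leading to discontinuation

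*SAP*

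**What the plan says.** SAP 10.2.1 defines a treatment-emergent ADE (TEADE) as a device-related event starting on or after the first self-injection and "through the final self-administration of study treatment + 7 days". SAP 3.8 (item 1) describes the same period as last dose plus 7 days. SAP 10.2.1 then states: "Only treatment-emergent ADEs will be included in the summary tables". Protocol 14.5 carries the same restriction. The planned summaries include "Incidence of TEADEs leading to discontinuation". The last item on that list sends everything else to a listing: "Incidence of non-TEADEs (only listed and not summarized in a table".

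Four other places bear on the point:

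- **Timing of Week 4.** Protocol Table 5-1, footnote a: "Visit windows are ±7 days from the scheduled visit day (relative to the first dose) at all visits except Visit 2a". Table 5-2, footnote a, limits the interval between doses to 21 to 35 days.
- **Definition of a safe self-injection.** SAP 11.1 requires "no SADEs and/or ADEs leading to withdrawal from the DV0004 substudy", with no limit on onset date. Protocol 4.1.1 and SAP 2.2.1.1 say the same.
- **Denominator.** SAP 3.1, for outcome and safety variables unless otherwise specified: "percentages will be summarized based only on those subjects with observed data for the variable being summarized".
- **COVID-19 breakdown.** SAP 10.2.2: "ADEs leading to discontinuation will be presented by COVID-19 enrollment period". Here the text says ADEs, not TEADEs.

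**The concern.** The end of the TEADE window is tied to an event that the ADE can prevent. If the second self-injection goes ahead, the window extends beyond it. If the ADE stops it, the window ended 7 days after Baseline. An ADE can thus drop out of the discontinuation table because it led to discontinuation.

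The situation is foreseen. Protocol 6.3 describes subjects who leave DV0004 because a medical condition or personal preference rules out further self-injection, and who stay in PA0012.

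The table matters because withdrawal due to an ADE is part of the plan's own definition of an unsafe self-injection. A subject who does not self-inject at Week 4 has no Week 4 result, so the observed-data primary percentage does not count this withdrawal. The discontinuation table is where it would be shown as device-related, and that table can read zero when such a withdrawal has occurred.

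**Working it through.** **Inputs.** Baseline self-injection = Day 0. Week 4 self-injection = Day 28, permitted range Day 21 to Day 35 (Protocol Tables 5-1 and 5-2, footnote a). Window end = last self-injection + 7 days (SAP 10.2.1). About 100 subjects per arm (SAP 2.3.6).

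**The plan's own figure.** SAP 2.3.3 places the device follow-up call 1 week after the last self-injection, at Week 5: 28 + 7 = 35 days = Week 5. This holds only for a subject who self-injects at Week 4. After a Baseline injection alone, the same rule gives 0 + 7 = Day 7.

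**Rule.** An ADE is a TEADE if 0 ≤ onset day ≤ day of last self-injection + 7.

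| Onset day | Injected at Baseline only (window to Day 7) | Injected on Days 0 and 28 (window to Day 35) |
|---|---|---|
| 3 | TEADE | TEADE |
| 7 | TEADE | TEADE |
| 8 | listed only | TEADE |
| 14 | listed only | TEADE |
| 27 | listed only | TEADE |

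**Length of the gap.** For a subject who does not take the second self-injection, the uncovered onset days run from Day 8 to the day before the planned visit.

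| Planned Week 4 day | Uncovered onsets | Days | Share of interval | Window after two injections |
|---|---|---|---|---|
| 21 | Days 8–20 | 13 | 13/21 = 62% | Days 0–28 = 29 days |
| 28 | Days 8–27 | 20 | 20/28 = 71% | Days 0–35 = 36 days |
| 35 | Days 8–34 | 27 | 27/35 = 77% | Days 0–42 = 43 days |

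After one injection the window is Days 0–7, or 8 calendar days. These are lengths of calendar time, not measures of risk.

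**Does another rule restore the event?**

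- SAP 4.2 imputes partial dates and treats ambiguous cases as treatment-emergent. It does not reach an ADE with a complete date.
- The closing paragraph of SAP 10.2.1, on ADEs that began before Week 4, governs ongoing status and end dates. It does not change who has a TEADE.
- SAP 3.8 speaks of the last dose rather than the final self-injection. The two could differ for a subject who moves to personnel-given doses in PA0012, but SAP 10.2.1 is the operative definition.

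**Effect on the table.** The documents give no rate, so the counts are assumptions. With 0, 1 or 2 omitted subjects in an arm of 100, the table is too low by 0/100 = 0, 1/100 = 1 or 2/100 = 2 percentage points. For scale only, exact binomial 90% intervals are 0 to 2.95% for 0 of 100, 0.05 to 4.66% for 1 of 100, and 0.36 to 6.16% for 2 of 100.

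**The case against.** The window is deliberate. It matches the device follow-up call, which comes 1 week after the subject's own last self-injection, including for those who withdraw. It is disclosed in SAP 3.8, and limiting tables to treatment-emergent ADEs implements Protocol 14.5. The gap also needs a narrow chain of events. Onset date decides inclusion, so an ADE starting on Days 0 to 7 that leads to a later withdrawal is already counted. What is left is a new onset more than 7 days after one observed, single-use injection, attributed to the device or its use, that also causes withdrawal.

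Nor is the event lost. All ADEs are listed, and SAP 5.1 tabulates reasons for discontinuation by device group. The secondary outcome judges the Baseline injection by the same criteria, including absence of ADEs leading to withdrawal. Finally, the same gap affects the tables of serious TEADEs and TEADEs leading to death, so changing one table is piecemeal.

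The rarity stands, and so does the point that listings keep the event. The rest does not remove the problem. A cut-off that suits the follow-up call still makes this table depend on the outcome it reports. The disposition summary is not specified to show whether a reason was device-related. SAP 11.2 scores the secondary outcome from the Baseline self-injection page of the case report form, which is not specified to pick up a later onset. The gap in the serious and death tables is a reason to go further, not to leave this table as it is.

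**Conclusion.** The concern holds. As written, SAP 10.2.1 omits from the discontinuation table a fully dated, investigator-attributed ADE that starts more than 7 days after a subject's only self-injection and causes the subject to leave DV0004. At the nominal visit this covers onsets on Days 8 to 27. The mechanism follows directly from the text. The consequence is modest: it is confined to descriptive safety tables, late onset after one observed injection is probably uncommon, and the true count may be zero.

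ADE occurrence is labelled the other safety variable in Protocol 4.1.3.4 and SAP 2.2.1.3.4. The label of primary safety endpoint appears only in the COVID-19 text (SAP 3.8.1 and 10.2.2), so no more weight should be put on it. The change should be made because the omission depends on the outcome being tabulated and is cheap to remove.

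**What to change.** In SAP 10.2.1, redefine this one table as *ADEs leading to discontinuation of DV0004*. Include every investigator-attributed ADE with onset on or after the first self-injection that led to discontinuation, whether or not it falls within the 7-day cut-off, and footnote those that are not TEADEs. No end date is needed, because an ADE that makes a subject leave DV0004 must start before the subject leaves. Use the same definition for the breakdown in SAP 10.2.2, which also settles whether ADEs or TEADEs are meant there. Record the exception in SAP 3.8, since it departs from Protocol 14.5. The TEADE window and the other TEADE tables stay unchanged; the sponsor may wish to consider whether the serious and death tables need the same treatment.

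The cost is one table definition and footnote, matching wording in SAP 10.2.2, and one line in SAP 3.8. No new data are needed, because all adverse events are already in the common PA0012/DV0004 database (SAP 10.2). The drawback is that the table may hold events that are not TEADEs, so its count may not agree with the other TEADE tables; the footnote explains any difference.
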